6) Known cognitive decline at baseline (IQCODE)

The Short Form of the Informant Questionnaire on Cognitive Decline in the Elderly (IQCODE) [4] is assessed at the patients baseline visit only. IQCODE is a 16 item questionnaire (variables *iqcode1 – iqcode16*), each question has a possible range of scores from 1 to 5. To obtain the mean IQCODE score for each participant take the mean of all IQCODE items available for that participant. Participants will still have their mean IQCODE score calculated if they are missing several items, participants will only be missing their mean IQCODE score if they are missing every item. Randomisation was stratified by IQCODE score ≥ 3.5

7) Quality of life at baseline and 6 months

Quality of life is measured by EQ-5D-5L scores [5], and is assessed at baseline and 6 months follow-up. EQ-5D-5L index scores will be computed as per the EQ-5D-5L user guide (version 2.1 April 2015).

8) Quality adjusted survival at 6 months and 12 months

Quality adjusted survival will be analysed as part of the economic evaluation and the methods will be detailed in a separate analysis plan.

9) Length of hospital stay over 6 months from randomisation

Number of nights spent in hospital between baseline and 6 months follow-up is collected on the health service use CRF.

10) Readmission or transfer to hospital at 1 month and 6 months

Subsequent admissions to hospital is measured at 1 month, and 6 months follow-up (variable *hadmityn*). Subsequent admissions to hospital is a binary variable (0 = No, 1 = Yes). The 6 months admission to hospital data will include the data collected at the 1 month time point. Number of days spent in hospital at 1 month, and 6 months after baseline will not be considered in the main statistical analysis, this data will be analysed as part of the economic evaluation and the methods will be detailed in a separate analysis plan.

11) Resource use (health and social care and informal care) at baseline and 6 months

Resource use will be analysed as part of the economic evaluation and the methods will be detailed in a separate analysis plan.

12) Costs and cost-effectiveness

Costs and cost-effectiveness will be analysed as part of the economic evaluation and the methods will be detailed in a separate analysis plan.

13) 'Living at home' at 12 months

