Mortality is measured at 3 days, 5 days, 1 month, 6 months, and 12 month follow-up (*deathyn*) and is a binary variable (0 = dead, 1 = alive). The mortality outcome will be summarised at each time point but will only be analysed at 6 and 12 months. The mortality at 12 months outcome will be analysed separately from the 6 months analysis and will not be reported in the main report, instead it will be reported in a separate statistical analysis report. Mortality at 6 months will be reported in the main statistical analysis report. A generalised linear mixed model will be fitted to the data similar to the primary analysis (see section 4.1) with mortality as the dependent variable. The model will include intervention arm, stratification factors (gender and known cognitive decline (IQCODE)) as fixed effects; and centre as a random effect. The adjusted relative risk and 95% CI and p-value for mortality at each time point will be estimated from the model. Mortality at 12 months will be analysed similar to the 6 months mortality data.

4) New long-term residential care at 1 month and 6 months

New long-term residential care is measured at 1 month and 6 months follow-up (*admitryn*) is a binary variable (0 = No, 1 = Yes). A generalised linear mixed model will be fitted to the data with new long-term residential care at 1 and 6 months as the dependent variable. The model will include intervention arm, gender, and known cognitive decline (IQCODE) as fixed effects, and centre as a random effect. The model will include a random intercept for each patient. The model will include an interaction between time and randomised group as a fixed effect. The adjusted relative risk with 95% CI and p-values for new long-term residential care at 1 month and 6 months will be estimated from the model.

5) Cognitive impairment at 6 months (MoCA)

Cognitive impairment measured at baseline and 6 months by the Montreal Cognitive Assessment (MoCA). This is converted into a binary variable (see section 2.1.2). A generalised linear mixed model will be fitted to the data with cognitive impairment at 6 months as the dependent variable. The model will include intervention arm, baseline MoCA score, gender, and known cognitive decline (IQCODE) as fixed effects; and centre as a random effect. The adjusted relative risk with 95% confidence intervals and p-value for cognitive impairment at 6 months will be estimated from the model.

6) Activities of daily living at 6 months (Barthel index)

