Activities of daily living is measured at baseline and 6 months by the Barthel index and is a continuous variable. A linear mixed effects model will be fitted to the data with activities of daily living at 6 months as the dependent variable. The model will include intervention arm, baseline Barthel index score, gender, and know cognitive decline (IQCODE) as fixed effects, as well as centre as a random effect. The intervention effect with 95% confidence intervals and p value for activities of daily living at 6 months will be estimated from the model.

7) Readmission or transfer to hospital at 1 month and 6 months

Readmission or transfer at 1 month and 6 months (*hadmityn*) is a binary variable (0 = No, 1 = Yes). A generalised linear mixed model will be fitted to the data with readmission or transfer to hospital at 1

and 6 months as the dependent variable. The model will include intervention arm, gender, and known cognitive decline as fixed effects, and centre as a random effect. The model will also include a random intercept for each patient. The adjusted relative risk with 95% CI and p-values for activities of daily living at 1 month and 6 months will be estimated from the model.

The distribution of the models will be assessed and the assumptions of the models will be checked. If any of the assumptions are violated the first option would be to apply a suitable transformation to the data, if this is not possible then a non-parametric test will be applied to the data (i.e. chi-Squared test). If a non-parametric test is adopted, it will not be possible to adjust for covariates.

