- 4) This sensitivity analysis will only be conducted when the 12 month follow-up data is available. The generalised linear mixed model in the primary analysis (see section 4.1) will be re-conducted with both the 'living at home' data at 6 months and 12 months as the outcome. The model will contain an additional fixed effects for the interaction between randomised group and time, so the treatment

effects and 95% CI can be obtained at each time point, along with the p-value. The model will include a random intercept for each patient to account for the repeated measures on the same patient. This will not be reported in the main analysis report, this will be reported in the additional statistical report containing the 12 month outcomes.

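### The readmission model in SAP section 5.1 item 7 has no time or time-by-group term, so it cannot give the separate 1-month and 6-month relative risks it promises, and its output line names the wrong outcome

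*SAP*

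**What the plan says.** Item 7 of SAP section 5.1 takes as its outcome "Readmission or transfer at 1 month and 6 months", a yes/no variable. The model terms are given in two sentences: "The model will include intervention arm, gender, and known cognitive decline as fixed effects, and centre as a random effect", and "The model will also include a random intercept for each patient". No other term is listed. The output sentence reads "The adjusted relative risk with 95% CI and p-values for activities of daily living at 1 month and 6 months will be estimated".

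Section 2.1.2 item 10 defines the variable cumulatively: "The 6 months admission to hospital data will include the data collected at the 1 month time point".

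Three other places in the SAP model a binary outcome at several times with a patient intercept:

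- Section 5.1 item 2 (delirium) and item 4 (new residential care) each state: "The model will include an interaction between time and randomised group as a fixed effect".
- Section 6 item 4 (living at home at 6 and 12 months) states "The model will contain an additional fixed effects for the interaction between randomised group and time, so the treatment" and goes on to say that effects and intervals can then be obtained at each time point.

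On the outcome named in the output sentence, section 5.1 item 6 says: "Activities of daily living is measured at baseline and 6 months by the Barthel index and is a continuous variable".

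**The concern.** The listed terms and the promised output do not match. Estimates specific to 1 month and to 6 months need a treatment effect that is allowed to differ by time, and item 7 lists nothing that does this. An analyst who follows the text literally has one relative risk and one p-value to report against two time points.

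The output sentence also names a different outcome, so taken literally the plan specifies no effect estimate for readmission at all.

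What is at stake is a named secondary outcome. Section 9.1 lists hospital admission among the potential risks for patients randomised to hospital at home. If the arms differ in the first month and then converge, a pooled figure would understate the early difference and overstate the later one.

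**Working it through.** **Step 1: one model or two?** The patient random intercept settles this. With one record per patient it has no role, so the text describes a joint model with two records per patient.

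**Step 2: what the joint model can estimate.** With arm as the only treatment term and no time term, the predicted risk within an arm, for given covariates, is the same at 1 and 6 months. There is one treatment parameter, whatever the link, and so one relative risk.

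**Step 3: is equal risk over time tenable?** No. A patient admitted by 1 month is counted as admitted by 6 months (section 2.1.2 item 10), so the risk can stay level or rise but not fall.

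**Step 4: what the single figure is.** Let c1 and c6 be the control risks and t1 and t6 the hospital-at-home risks. With a log link, complete records at both visits and covariates left out, each arm's fitted risk is its average over the two visits. Hence

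pooled RR = (t1 + t6) / (c1 + c6) = w1 × RR1 + w6 × RR6, where w1 = c1/(c1 + c6) and w6 = c6/(c1 + c6).

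Because c6 is at least c1, the 6-month value always carries at least half the weight.

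**Step 5: numbers.** The SAP gives no readmission rates, so all risks below are assumptions.

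| Control vs hospital at home, 1 month | Control vs hospital at home, 6 months | True RRs | Pooled RR |
|---|---|---|---|
| 20% vs 30% | 50% vs 50% | 1.50, 1.00 | 0.80/0.70 = 1.14 |
| 20% vs 20% | 50% vs 60% | 1.00, 1.20 | 0.80/0.70 = 1.14 |
| 15% vs 22.5% | 45% vs 40.5% | 1.50, 0.90 | 0.63/0.60 = 1.05 |
| 20% vs 22% | 45% vs 46% | 1.10, 1.02 | 0.68/0.65 = 1.05 |

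In the first row the weights are 0.20/0.70 = 0.286 and 0.50/0.70 = 0.714, and 0.286 × 1.5 + 0.714 × 1.0 = 1.14. The first two rows give the same pooled figure from opposite patterns: an early difference that disappears, and a late difference that was not there at 1 month.

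**Step 6: check by fitting.** The first three rows were also fitted as Poisson log-link models to constructed data. The arm sizes follow from the SAP's 1050 less 6% attrition: 1050 × 0.94 = 987, or 329 control and 658 hospital at home. Group only gave 1.14, 1.15 and 1.05 (the second differs from the table because counts were rounded to whole patients). Adding a time main effect alone left these values unchanged. Adding time by group gave 1.49 and 1.00, 1.00 and 1.20, and 1.51 and 0.90, which match the true pairs apart from rounding.

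**Step 7: the label.** Activities of daily living is a continuous score measured at baseline and 6 months (section 5.1 item 6 and Appendix II). A 1-month relative risk for it cannot exist.

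**The case against.** The strongest reply is that this is a drafting slip with obvious intent. Item 4 has the same time points, the same structure and the same promised output, plus the interaction sentence. The misplaced label looks like a carry-over from item 6. An analyst would probably notice both and add the missing term. This stands as a reason to keep the point modest. It does not remove it: the plan as written cannot produce its stated output, and a pre-specified model should not have to be inferred from a neighbouring item.

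A second reply is that the size depends entirely on assumed risks. That is also fair. In the mild example the pooled 1.05 is close to both true values.

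A reader might go further in four ways that the SAP does not support:

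- **That the residential-care model is also wrong**, because its outcome is cumulative too and it has a patient intercept. That model already has the interaction. In random-intercept log-link fits to fully cumulative data with the interaction, the intercept variance went to zero and the assumed relative risks were recovered (for example 1.50 and 1.00). Standard errors and other links were not examined, so no fault has been shown.
- **That separate mortality models show the SAP's preference for cumulative outcomes.** The 12-month mortality analysis is separate because it goes into a later report (section 5.1 item 3; section 11). For living at home, which includes death, section 6 item 4 plans a joint model.
- **That early transfer is a key question of the trial.** The SAP lists readmission or transfer as one of many secondary outcomes.
- **That the pooled figure is wrong at both times.** That requires the two true relative risks to differ.

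**Conclusion.** The point holds for item 7 alone. As specified, the readmission model gives one pooled relative risk and cannot give the two it promises. It treats the risk as constant between 1 and 6 months although the variable is cumulative, and its output sentence names another outcome.

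The numerical consequence is conditional. If the relative risk is the same at both times, the single estimate does not misstate it. If it differs, the estimate is a weighted average leaning towards the 6-month value: about 1.14 for assumed values of 1.5 and 1.0, and about 1.05 for 1.10 and 1.02. These figures rest on assumed risks, a log link and complete records at both visits. That there is only one relative risk rests on none of these; it follows from the listed terms.

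This should be corrected, but it concerns a secondary outcome whose intended model can be guessed. It does not touch the primary analysis, and no change to the residential-care model is claimed.

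**What to change.** In section 5.1 item 7:

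- Add time and the time-by-randomised-group interaction as fixed effects, in line with item 4, and state that the 1-month and 6-month relative risks are obtained from that model. Alternatively, fit a separate model at each time point and drop the patient intercept.
- In the output sentence, replace activities of daily living with readmission or transfer to hospital.

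The cost is two or three sentences of SAP wording. No extra data are needed.

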5.2 TERTIARY/OTHER OUTCOMES

Analysis of other outcomes (i.e. cost-effectiveness, process evaluation and qualitative interviews) will be detailed elsewhere.

6 SENSITIVITY ANALYSIS

Sensitivity analysis will be conducted with respect to the primary outcome only (unless explicitly stated) and will explore the sensitivity of results to different assumptions regarding missing data, outliers and departure from randomisation policy.

- 1) The generalised linear mixed model assumes that the data is missing at random (MAR). A logistic regression analysis will be conducted to investigate factors at baseline (if any) that are predictive of non-response. If any factors are associated with non-response, the generalised linear mixed model in the primary analysis will be re-run with these factors included as fixed covariates in the model.
- 2) Some patients might have missing data for the 'living at home' at 6 months outcome due to missing place of assessment and/or death status. These patients will have their missing place of assessment and/or death status replaced with each of the alternatives for these variables:
 - i) Living at home and alive
 - ii) Not living at home and alive
 - iii) Dead

The 'living at home' at 6 months outcome will be re-derived, and the generalised linear mixed model in the primary analysis in section 4.1 will be re-conducted with each of these replacements to the outcome.

- 3) Some patients might have missing data for the 'living at home' at 6 months outcome due to missing place of assessment and/or death status. Patients with missing 'living at home' at 6 months outcome will have their missing place of assessment and/or missing death status imputed using multiple imputation (MI). A fully inclusive MI will be conducted with; gender, age, education, place of baseline assessment, if consent signed by 'consultee', and other factors expected to relate to the main outcome (i.e. practice, presenting problems at baseline, diagnosis of delirium at baseline) as covariates. The primary outcome will then be re-derived using the same method as in section 2.1.1. The generalised linear mixed model in the primary analysis in section 4.1 will be repeated for the imputed dataset and the results compared to those from the primary analysis.
- 4) This sensitivity analysis will only be conducted when the 12 month follow-up data is available. The generalised linear mixed model in the primary analysis (see section 4.1) will be re-conducted with both the 'living at home' data at 6 months and 12 months as the outcome. The model will contain an additional fixed effects for the interaction between randomised group and time, so the treatment

effects and 95% CI can be obtained at each time point, along with the p-value. The model will include a random intercept for each patient to account for the repeated measures on the same patient. This will not be reported in the main analysis report, this will be reported in the additional statistical report containing the 12 month outcomes.

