2.3 SAMPLE SIZE

The sample size is calculated for the primary outcome: living at home at 6 months follow up (the inverse of death or living in a residential care setting), for a 2:1 randomisation ratio with 2/3rd randomized to admission avoidance HAH with CGA and 1/3 to inpatient CGA. Several sources informed our estimate of effect size; these were one of the trials included in the IPD meta-analysis of HAH which recruited frail older people who required hospital level care (similar to the study population we plan to recruit), an audit of 750 patients who received HAH + CGA in Lanarkshire, the RCTs of CGA included in the Cochrane Review and the pooled estimate for the relative effect at 6 months obtained from the IPD Cochrane Review of HAH (3 trials, 607 participants) which was an adjusted Hazard Risk of 0.62 (95% CI 0.45 to 0.87) for mortality. Our proposed study effect estimate is based on a control group (CGA hospital) event rate at 12 months of 50% with a 10% reduction in living in a residential setting to 40% in the CGA at home group, equal to a relative risk of 0.8 which lies towards the top end of the 95% CI for the pooled estimate. We have calculated that a sample size of 1050 to achieve around 83% power at a significance level of 0.05 to detect a 10% absolute difference, assuming a control group event rate at 12 months of 50% and 6% attrition.

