4.2 HANDLING MISSING DATA

The frequency (with percentage) of losses to follow-up (defaulters and withdrawals) over the 6 months of the study will be reported by randomised group and compared between the groups.

The availability of the outcome data for the primary outcome will be summarised by randomised group. The generalised linear mixed model implicitly accounts for data missing at random, however the data missing mechanism will be explored. A logistic regression model will explore any association between baseline characteristics and availability of the primary outcome.

Any changes to the assumptions made in the primary analysis i.e. data missing at random, will be considered in a sensitivity analysis.

The impact of any missing primary outcome data on the primary analysis will be assessed by carrying out a sensitivity analyses based on imputing (multiple imputation) the missing values.

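### The covariate-adjusted re-run in section 6 item 1 depends on a non-response screen with no arm-by-factor term, so loss that differs by arm can go unnoticed (minor)

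*SAP*

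**What the plan says.** Section 4.2 of the SAP plans a model for missingness: "A logistic regression model will explore any association between baseline characteristics and availability of the primary outcome". It also has losses to follow-up tabulated by arm; these "will be reported by randomised group and compared between the groups".

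Section 6 item 1 turns the same model into a decision rule. First, "A logistic regression analysis will be conducted to investigate factors at baseline (if any) that are predictive of non-response". The consequence follows: "If any factors are associated with non-response, the generalised linear mixed model in the primary analysis will be re-run with these factors included". The flagged factors enter that model as further fixed effects.

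Neither place names randomised arm, an arm-by-factor term or separate fits by arm. Neither gives a threshold for association or a list of candidate factors, and neither requires a flagged factor to be related to living at home. The primary model in section 4.1 already contains arm, gender, the full IQCODE score and centre. Items 2 (replacing missing outcomes with each alternative in turn) and 3 (multiple imputation) do not depend on the screen.

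**The concern.** In a randomised comparison, a baseline factor that predicts loss equally in both arms leaves the completers balanced on it. Imbalance, and so bias, arises when the factor predicts loss differently in the two arms and also predicts the outcome. A regression of non-response on baseline factors alone tests neither condition. If the factor raises loss in one arm and lowers it in the other, the two associations can offset each other and the factor is not flagged.

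What is at stake is how far item 1 can be relied on. It is the only planned covariate-adjusted repeat of the primary model, and whether it runs, and with which covariates, is left to a data-driven test. The by-arm totals in section 4.2 show how many patients were lost in each arm, but not which kinds of patient. The trial is open and the care settings differ, so arm-specific loss is a reasonable thing to check for.

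**Working it through.** **The plan's own figures.** Section 2.3 gives N = 1050 ("We have calculated that a sample size of 1050 to achieve around 83% power at a significance level of 0.05"), 2:1 allocation, 50% against 40%, "assuming a control group event rate at 12 months of 50% and 6% attrition". Evaluable: 1050 × 0.94 = 987, that is 329 control and 658 HAH. Two-sided power at 0.05 for two proportions is 84.8%, or 83.1% with continuity correction, so the stated figure reproduces and is not in dispute. The expected number of non-responders is 1050 × 0.06 = 63. The SAP gives no figure for the screen itself.

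**Assumed example (not SAP figures).** One binary factor outside the primary model, present in 40%. Control probability of living at home is 62% without it and 32% with it, so 0.6 × 0.62 + 0.4 × 0.32 = 0.50. The true RR is 1.20 in both strata (74.4% and 38.4%; overall 0.60). There are 350 control and 700 HAH patients. Within arm and factor level, loss is unrelated to outcome.

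For an arm with loss m1 (with factor) and m0 (without), the completers' probability is

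[0.6(1 − m0)r0 + 0.4(1 − m1)r1] / [0.6(1 − m0) + 0.4(1 − m1)].

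*Opposite-direction loss* (control 15% with, 2% without; HAH 2% with, 8% without):
- Control: (0.588 × 0.62 + 0.340 × 0.32) / 0.928 = 0.5101.
- HAH: (0.552 × 0.744 + 0.392 × 0.384) / 0.944 = 0.5945.
- RR = 0.5945 / 0.5101 = 1.166; difference 8.4 points instead of 10.
- Loss: control 7.2%, HAH 5.6%, overall (7.2 + 2 × 5.6)/3 = 6.1%.
- Pooled loss with the factor: (15 + 2 × 2)/3 = 6.3%. Without it: (2 + 2 × 8)/3 = 6.0%.
- Pooled log OR = 0.058; SE = √[1/(420 × 0.0633 × 0.9367) + 1/(630 × 0.06 × 0.94)] = 0.261. A 5% test on this has almost no power; in 4,000 simulated trials it fired in about 5%.
- SE of log RR = √[0.490/(0.510 × 324.8) + 0.4055/(0.5945 × 660.8)] = 0.063. Bias = ln(1.20/1.166) = 0.029, about 0.46 SE.

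The same formulas, with other loss patterns (loss with / without the factor):

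| Control | HAH | Overall loss | Completers' RR | Screen fires |
|---|---|---|---|---|
| 12% / 2% | 12% / 2% | 6.0% | 1.200 | 100% |
| 15% / 2% | 2% / 8% | 6.1% | 1.166 | about 5% |
| 12% / 2% | 3% / 7% | 5.6% | 1.175 | 7% |
| 10% / 2% | 5% / 6% | 5.5% | 1.184 | 28% |
| 15% / 2% | 6% / 8% | 7.2% | 1.173 | 45% |
| 15% / 2% | 2% / 2% | 3.7% | 1.176 | 93% |
| 30% / 4% | 4% / 16% | 12.3% | 1.127 | 5 to 6% |

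A factor-by-arm test fired in 3%, 100% and 84% of trials for rows 1, 2 and 4.

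**Second set of assumptions.** Prevalence 50%, control risk of not living at home 30% without and 70% with the factor, true RR 0.80 for that event, about 6% loss (with / without):
- Opposite directions, control 2% / 10%, HAH 8% / 4%: RR 0.780, screen fires in 5%; the factor-by-arm test fires in 98%.
- Factor acts in control only, 16% / 2% against 4.5% / 4.5%: RR 0.825, screen fires in 89%.
- Factor acts in HAH only, 6% / 6% against 10% / 2%: RR 0.786, screen fires in about 95% to 97%.
- Same loss in both arms, 10% / 2%: RR 0.800, screen fires in about 100%. On the living-at-home scale the RR moves slightly, from 1.200 to 1.193.

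In the control-only and HAH-only patterns, adding the factor to the model corrects the estimate.

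**The case against.** A reader might infer that item 1 acts only when missingness is harmless and fails when it is harmful. The SAP and the figures do not support that. When loss is concentrated in one arm the screen fires in most trials (89% to 97% above), and the added covariate removes the bias. Firing on harmless loss costs one extra covariate in a sensitivity model. Silence needs near-opposite loss in the two arms, or low power. Raising one cell of the example (HAH loss with the factor from 2% to 6%) lifts the firing rate from about 5% to 45%. Nothing in the SAP suggests that opposite-direction loss is expected.

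A reader might also infer that a biased primary result could pass with no other check. That is not so either. Item 3 imputes unconditionally, from a list that includes baseline delirium, place of baseline assessment and consultee consent. In the opposite-direction example, imputation from the factor with arm left out brings the RR from 1.166 back to about 1.187. Gender and IQCODE, which may be strong predictors, are already in the primary model.

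Finally, the absence of an arm term is read from silence; the SAP does not exclude one.

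Most of this stands and limits the point. What it does not remove: item 3 does not list arm among its imputation covariates, and item 2 as written does not vary the replacement by arm, so neither is a complete substitute. An arm main effect alone in the non-response model would not reveal a factor that acts differently by arm.

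**Conclusion.** The point holds in a limited form. As written, the screen does not look for loss that differs by arm, does not ask whether a factor is prognostic, and has no threshold or candidate list, yet it decides whether the adjusted re-run takes place. Under assumed opposite-direction loss at about 6% attrition the RR is about 1.17 against a true 1.20, roughly half a standard error, and the screen fires in about 5% of trials. At about 12% attrition, double the plan's figure, the same pattern gives 1.13.

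These sizes rest on assumed prevalence, outcome risks and loss patterns, on a single factor outside the primary model, and on a 5% test that the SAP does not specify. Severity is minor: one of several sensitivity analyses is affected, and the primary estimate is unchanged.

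**What to change.** In section 6 item 1, remove the condition. State that the section 4.1 model will always be re-run with a pre-specified list of baseline factors expected to relate to living at home. The factors that item 3 already names would serve: age, education, place of baseline assessment, consultee consent, presenting problem and baseline delirium.

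In section 4.2 and item 1, fit the non-response model with randomised arm and arm-by-factor terms, or separately by arm, and use it to describe missingness, not to select covariates.

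The cost is SAP wording and one model run. The downsides are a few more parameters, possible convergence problems in a mixed model on the relative-risk scale (so a fallback should be named), and a simple rule for missing baseline values.

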2.1.1 PRIMARY OUTCOME FOR THE PRIMARY OBJECTIVE

The primary outcome is 'living at home' at 6 months.

Living at home is defined as the inverse of death or living in a residential care setting. It is derived from a place of assessment variable, (a 5-category variable, 1 = hospital assessment centre, 2 = in-patient hospital, 3 =

residential care home, 4 = patient's home, and 5 = other) and the patient's death status (0 = alive, 1 = dead) reported at the 6 months visit. Living at home will be coded as a binary variable (1 = alive and living at home, 0 = otherwise (including deaths and living at residential care). Living at home will be computed as 0 if death status = 1 (dead) or place of assessment = 3 (residential care home), or place of assessment = 5 (other) and other = "Nursing Home" (variable *assessoth6m*), otherwise living at home = 1, as long as patient also has a visit date for the particular time point.

Additional information about the residential care (variable *admitryr*) will be used for patients with a place of assessment = 1 (hospital assessment centre) or = 2 (in-patient hospital) to verify where these patients were admitted from. If patients have been in residential care they will be coded as 'not living at home', if patients are not recorded as having been in residential care then they will be assumed to have been admitted from 'home'.

If the patient's death status is missing and the patient's place of assessment has been completed, the patient will be assumed to be alive. In cases where the place of assessment and death status are conflicting (i.e. place of assessment is complete but the patient has been reported as dead) then the patient death form CRF will be used to confirm whether the patient is alive or dead. If the place of assessment and the patient's death status are both missing, then the primary outcome will be missing. This information will be coded as a binary variable (0 = death or not living at home, 1 = alive and living at home) to be used in the analysis.

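### The missing-outcome checks hold only two distinct scenarios, none differing by arm, and the listed imputation model omits randomised arm and IQCODE

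*SAP*

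**What the plan says.** SAP section 2.1.1 defines the primary outcome as binary. The lower code covers every unfavourable state: "0 = otherwise (including deaths and living at residential care". The outcome is missing only when place of assessment and death status are both missing.

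SAP section 4.2 says that departures from missing at random (MAR) will be considered in a sensitivity analysis. Section 6 gives three checks on the 6-month data:

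- Item 1 adds baseline predictors of non-response to the primary model.
- Item 2 replaces missing values: "These patients will have their missing place of assessment and/or death status replaced with each of the alternatives for these variables". The alternatives are (i) at home and alive, (ii) "Not living at home and alive", and (iii) dead. The binary outcome is re-derived and the primary model refitted each time. No version differs by arm.
- Item 3 is multiple imputation: "A fully inclusive MI will be conducted with; gender, age, education, place of baseline assessment, if consent signed by" a consultee, followed by practice, presenting problems and baseline delirium. Randomised arm and IQCODE are not listed.

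The primary model in section 4.1 contains arm, gender, the full IQCODE score and a random centre effect. Section 2.4 states that neither participants nor the nurses collecting outcomes can be blinded.

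**The concern.** Items 1 and 3 both assume MAR, so item 2 is the only check that departs from it. Two of its three scenarios lead to the same data, so a report would show three results where only two are separate. Both distinct scenarios also treat a missing HAH patient and a missing inpatient-arm patient alike. In an open trial the reasons for loss may differ by arm, and the plan has no scenario for that.

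Item 3 has a separate problem. An imputation model should contain the terms of the analysis model, above all the one whose effect is being estimated. If arm is left out, missing outcomes in both arms are drawn from a common rate and the two arms are pulled together. A gap between the imputed and primary results could then be read as sensitivity to missing data when part of it comes from the imputation model itself.

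**Working it through.** **Inputs.** Section 2.3 plans 1050 patients for about 83% power at the 5% level. Its control rate and loss are stated as "assuming a control group event rate at 12 months of 50% and 6% attrition". The event rate in the other arm is put at 40%, so living at home is 50% (inpatient) versus 60% (HAH). With 2:1 allocation, 1050 splits into 700 HAH and 350 inpatient.

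**The plan's own figure.** Take a two-sided test (assumed; the SAP does not state sides), 83% power and a continuity correction.
- Pooled rate = (0.5 + 2 × 0.4)/3 = 0.4333.
- Uncorrected controls = [1.960 × √(0.4333 × 0.5667 × 1.5) + 0.954 × √(0.25 + 0.24/2)]² / 0.1² ≈ 313.2.
- Continuity-corrected controls = (313.2/4) × [1 + √(1 + 2 × 3/(2 × 313.2 × 0.1))]², which rounds up to 329.
- Total = 3 × 329 = 987, and 987/0.94 = 1050. The stated size is reproduced.

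**Coding of the scenarios.** (i) gives 1. (ii) gives 0 because the patient is not at home. (iii) gives 0 because the patient is dead. So (ii) and (iii) produce the same dataset.

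**Replacement scenarios, 6% missing in each arm.** This leaves 42 and 21 missing, 658 and 329 observed, and expected counts at home of 0.6 × 658 = 394.8 and 0.5 × 329 = 164.5. With a and b at home out of n₁ and n₀, RR = (a/n₁)/(b/n₀) and SE(log RR) = √(1/a − 1/n₁ + 1/b − 1/n₀). These are crude, without covariates or centre.

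| Missing set to | HAH | Inpatient | RR (95% CI) | Difference |
|---|---|---|---|---|
| Observed only | 394.8/658 | 164.5/329 | 1.200 (1.059–1.359) | 10.0 points |
| (i) all at home | 436.8/700 | 185.5/350 | 1.177 (1.050–1.320) | 9.4 |
| (ii) and (iii) | 394.8/700 | 164.5/350 | 1.200 (1.055–1.365) | 9.4 |
| HAH not home, inpatient home | 394.8/700 | 185.5/350 | 1.064 (0.945–1.198) | 3.4 |
| HAH home, inpatient not home | 436.8/700 | 164.5/350 | 1.328 (1.171–1.505) | 15.4 |

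**Unequal loss (assumed).** With 8% HAH and 2% inpatient missing (56 and 7), (ii)/(iii) gives 1.127 (0.993–1.278). With 3% and 12% missing (21 and 42), (i) gives 1.093 (0.979–1.220) and (ii)/(iii) gives 1.323 (1.157–1.512). The planned scenarios do respond here.

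**Imputation without arm.** Missing outcomes are drawn at about the pooled rate, (2 × 0.6 + 0.5)/3 = 0.567. Baseline covariates are balanced by randomisation and cannot stand in for arm. With a fraction m missing in each arm, the expected difference is (1 − m) × 10 points:
- m = 6%: (0.94 × 0.6 + 0.06 × 0.567) − (0.94 × 0.5 + 0.06 × 0.567) = 0.598 − 0.504 = 9.4 points.
- m = 10%: 9.0 points. m = 20%: 8.0 points.

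Simulated RRs (20 imputations, 1000 replicates), without versus with arm, were 1.191 versus 1.205 at 6%, 1.175 versus 1.196 at 10%, and 1.154 versus 1.197 at 20%.

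**The case against.** **The checks are not blind to bias.** A reader might infer that these analyses will reassure whatever the missingness mechanism. The SAP does not support that. The unequal-loss results above show that same-value replacement can carry the interval across 1. Section 4.2 also compares losses between arms and models availability of the outcome, and item 1 refits with predictors of non-response. This stands. The gap is limited to missingness that differs in meaning, not amount, by arm.

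**The opposite-arm results are extremes.** They need every missing patient in one arm to be at home and every one in the other not. Section 2.1.2 has the trial manager check with the site when neither the follow-up form nor the death form is complete, so unknown vital status should be uncommon. This also stands: the extremes are bounds, not likely values.

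**The imputation wording may be loose.** The list is described as inclusive, arm could be added in practice, and practice may be a slip for centre. But the listed covariates are the specification, and neither arm nor IQCODE is among them.

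**Invalid variance.** The reference to one imputed dataset might suggest single imputation. Sections 4.2 and 6 both say multiple imputation, so the singular is more likely loose drafting. In a simulation of imputation without arm, pooled by Rubin's rules with no covariates, coverage of the true 10 points was about 95% to 96% at 6%, 10% and 20% missing. What remains is that the SAP states no pooling rule.

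**Conclusion.** The point holds as a weakness in prespecified secondary checks. The primary analysis is untouched. Section 6 item 2 contains two distinct scenarios, not three, and neither tests a departure from MAR that differs by arm. At the planned 6% attrition they keep the relative risk between 1.18 and 1.20, while opposite-arm bounds run from 1.06, with an interval that includes 1, to 1.33.

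The imputation model as listed is not compatible with the primary model and biases towards no effect. At 6% missing this is small (RR about 1.19 versus 1.20, or 9.4 versus 10 points); it would matter more if losses were well above plan. The missing arm-specific scenarios are the larger issue.

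The sizes rest on planning rates that the SAP states for 12 months and that are used here at 6 months, on 6% missing in each arm, and on crude calculations without covariates or centre.

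**What to change.** 1. In section 6 item 2, replace scenario (iii) with two opposite-arm scenarios: missing HAH patients not at home with missing inpatient-arm patients at home, and the reverse. Alternatively, use a tipping-point grid over the imputed proportion at home in each arm. Label the opposite-arm results as worst-case bounds.
2. In item 3, include randomised arm in the imputation model, or impute separately by arm. Add IQCODE, and name centre where the list says practice.
3. State that the primary model is fitted to each imputed dataset and that the results are pooled by Rubin's rules.

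The cost is SAP wording and a few extra model runs. No new data are needed.
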